3.3 Discontinuation from Study Treatment

Patients will be informed that they have the right to withdraw from the study at any time for any reason, without prejudice to their medical care. Patients will be discontinued from study treatment for any of the following reasons:

- Disease progression
- Irreversible or intolerable toxicity or abnormal laboratory values thought to be related to drug toxicity
- Conditions requiring therapeutic intervention not permitted by the protocol
- Intercurrent illness (this will be at the Investigator's discretion)
- Inability of the patient to comply with study requirements or lost to follow-up
- Patient requests to discontinue treatment
- Patient withdraws consent from the study
- Pregnancy
- Protocol violation

At the time of withdrawal, all study procedures outlined for the End of Study visit should be completed. The primary reason for patient's withdrawal from the study should be recorded in the source documents and eCRF. After discontinuation from protocol treatment, patients must be followed for AEs for 30 days after their last dose of study drug. All new AEs occurring during this period must be reported and followed until resolution, unless, in the opinion of the Investigator, these values are not likely to improve, because of the underlying disease. In this case, the Investigators must record his or her reasoning for this decision in the patients' medical records and as a comment in the electronic Case Report Form (eCRF).

All patients who have Grade 3 or 4 laboratory abnormalities (per National Cancer Institute Common Terminology Criteria for Adverse Events [NCI CTCAE] v4.0; <http://evs.nci.nih.gov/ftp1/CTCAE/CTCAE>), at the time of discontinuation must be followed until the laboratory values have returned to Grade 1 or 2, unless it is, in the opinion of the Investigator, not likely that these values are to improve. In this case, the Investigator must record his or her reasoning for making this decision in the patients' medical records and as a comment on the eCRF.

CONFIDENTIAL

STUDY DRUG: MLN9708
FINAL PROTOCOL: 11 APRIL 2014
AMENDMENT NUMBER 3: 11 FEBRUARY 2016

SCRI INNOVATIONS STUDY NUMBER: MM 42

VERSION 4

4. STUDY REGISTRATION

The patient must willingly consent after being informed of the procedures to be followed, the experimental nature of the treatment, potential benefits, alternatives, side-effects, risks, and discomforts. Human protection committee (Institutional Review Board [IRB]) approval of this protocol and consent form is required. Eligible patients who wish to participate in the study will be enrolled into the study.

Registration must occur prior to the initiation of protocol therapy. Patients eligible to participate in the study may be enrolled through the SCRI Innovations Central Enrollment Desk. The enrollment desk may be reached by calling [name]. Registration may be done via [contact] Monday through Friday, 8:30 a.m. to 4:30 p.m., Central Standard Time. Patient registration will be confirmed via email within 24 hours, or by the next business day.

5. STUDY DESIGN

This is a Phase II, open-label, multicenter, non-randomized study to determine the feasibility of MLN9708 as maintenance after allogeneic stem cell transplant for multiple myeloma. Patients will be enrolled between Days 45 and 120 after allogeneic transplant and will receive MLN9708 on Days 1, 8, and 15 of each 28-day cycle for 6 cycles. Up to 18 patients will be enrolled in the dose-escalation phase to define the MTD of MLN9708. An additional 20 patients will be enrolled in the expansion phase at the MTD.

Up to 5 study sites are planned in the United States.

Dosing will start at 2.3 mg. If acceptable tolerability is demonstrated, escalations will be made to 3 mg and to the maximum-planned dose (MPD) of 4 mg. Once the MTD/MPD is determined, enrollment into the expansion phase will proceed at that dose. The study schema is presented in Figure 1.

[figure not shown]
CONFIDENTIAL

STUDY DRUG: MLN9708
FINAL PROTOCOL: 11 APRIL 2014
AMENDMENT NUMBER 3: 11 FEBRUARY 2016

SCRI INNOVATIONS STUDY NUMBER: MM 42

VERSION 4

Figure 1 Study Schema

MTD = Maximum-tolerated dose
MPD = Maximum-planned dose

5.1 Treatment Plan

All protocol-specific criteria for administration of study drug must be met and documented before drug administration. Study drug will be administered or dispensed only to eligible patients under the supervision of the investigator or identified subinvestigator(s). Patients should be monitored for toxicity, as necessary, and doses of MLN9708 should be modified as needed to accommodate patient tolerance to treatment; this may include symptomatic treatment, dose interruptions, and adjustments of MLN9708 dose.

MLN9708 will be administered orally as monotherapy. Dosing will start at 2.3 mg. If acceptable tolerability is demonstrated, escalations will be made to 3 mg and to the MPD of 4 mg. Once the MTD is determined, enrollment of an additional 20 patients into the expansion phase will proceed at that dose.

MLN9708 will be given on an empty stomach, with no food and fluids except for water and prescribed medications for 2 hours before and 1 hour after each dose. Each dose of MLN9708 will be given orally with approximately 8 oz (240 mL) of water. Missed doses can be taken as soon as the patient remembers as long as the next scheduled dose is at least 72 hours from that point in time. A double dose should not be taken to make up for a missed dose. If the patient vomits after taking a dose, the patient should not be given a repeat dose, rather dosing should resume at the time of the next scheduled dose.

The capsules should not be chewed, broken, or opened for administration. Patients should be monitored for toxicity as necessary, and doses of MLN9708 should be modified on the basis of the patient's tolerability. This may include symptomatic treatment, dose interruptions, and/or adjustments of the MLN9708 dose. More conservative dose escalation, evaluation of alternative dosing, and expansion of an existing dose level are all permissible following discussions between

CONFIDENTIAL

STUDY DRUG: MLN9708
FINAL PROTOCOL: 11 APRIL 2014
AMENDMENT NUMBER 3: 11 FEBRUARY 2016

SCRI INNOVATIONS STUDY NUMBER: MM 42

VERSION 4

the Study Chair, Millennium, and the Investigators, if such measures are needed for patient safety or for a better understanding of the dose-related toxicity or exposure of MLN9708.

No routine prophylactic antiemetics will be given. However, antiemetics may be administered prior to treatment based on the patient's susceptibility to nausea and vomiting at the investigator's discretion, and may be given prophylactically afterwards.

5.1.1 Dose Escalation Procedure

The actual number of dose cohorts to be explored in this study will depend upon the MTD and the observed safety profile of MLN9708.

The 3 + 3 Dose-Escalation Design

Using a 3 + 3 dose escalation design, each cohort will enroll up to 6 evaluable patients. Evaluation of a cohort of at least 3 patients completing 1 cycle of treatment (28 days) is required prior to proceeding to the next dose level. Dose escalation decisions will take into account the safety profile of prior dose groups. Inpatient dose escalation will not be allowed.

The 3 + 3 dose escalation procedure is presented in Table 3.

Table 3 Dose Escalation (3 + 3) Design

Number of Patients with a DLT	Action
0 of 3 patients	Escalate to next dose level as shown in Figure 1
1 of 3 patients	Accrue 3 additional evaluable patients at the current dose level (for a total of up to 6 evaluable patients) ^a
1 of 6 patients	Escalate to the next dose level as shown in Figure 1
2 or more patients in a dose level group of up to 6 patients	The MTD has been exceeded.

DLT = Dose-limiting toxicity

^a For a patient to be considered "evaluable," he or she must have met the minimum safety evaluation requirements of the study, and/or experienced a DLT.

5.1.3 Maximum-Tolerated Dose

The MTD is the highest dose at which ≤ 1 of 6 patients experience a DLT during 1 cycle (28 days) of therapy. If 2 or more patients in a dosing group of ≤ 6 patients experience a DLT, the MTD has been exceeded. If 2 or more patients in a doses group of up to 6 patients experience a DLT and only 3 patients were evaluated at the previous (i.e., next lower) dose, then an additional 3 patients will be evaluated at this next lower dose and if zero or one have DLTs then this previous dose level is declared the MTD.

5.1.4 Expansion after Determination of the Maximum-Tolerated Dose

Once the MTD is determined, the MTD cohort of patients will be expanded with an additional 20 patients to further characterize the safety and clinical benefits of maintenance with MLN9708 after allogeneic stem cell transplant. If the MTD is not reached, the expansion will proceed at the MPD.

CONFIDENTIAL

STUDY DRUG: MLN9708
 FINAL PROTOCOL: 11 APRIL 2014
 AMENDMENT NUMBER 3: 11 FEBRUARY 2016

SCRI INNOVATIONS STUDY NUMBER: MM 42

VERSION 4

5.2 Treatment Duration

The total duration of the study from first patient enrolled to last patient out is planned to be approximately 3 years.

Based on tolerability, patients will receive 6 cycles of MLN9708 as maintenance therapy following an allogeneic stem cell transplant.

5.3 Concomitant Medications

Patients will be instructed not to take any additional medications during the course of the study without prior consultation with the research team. At each visit, the patient will be asked about any new medications he is taking or has taken after the start of the study drug.

5.3.1 Permitted Concomitant Medications and Procedures

The following medications and procedures are permitted during the study:

- Antiemetics, including 5-HT₃ serotonin receptor antagonists, may be used prior to treatment based on the patient's susceptibility to nausea and vomiting at the discretion of the investigator.
- Loperamide or other antidiarrheal should be used for symptomatic diarrhea at discretion of the investigator. The dose and regimen will be according to institutional guidelines. IVF should be given to prevent volume depletion.
- Growth factors (e.g., granulocyte colony stimulating factor [G-CSF], granulocyte macrophage-colony stimulating factor [GM-CSF], recombinant erythropoietin) are permitted in Cycle 1 of the dose escalation phase if the patient has a neutrophil value that meets DLT criteria and after Cycle 1 of the dose escalation phase. Their use should follow published guidelines and/or institutional practice.
- Erythropoietin will be allowed in this study according to standard clinical practice. Their use should follow published guidelines and/or institutional practice.
- Patients should be transfused with red cells and platelets in Cycle 1 of the dose escalation phase if the patient has a platelet value that meets DLT criteria and as clinically indicated and according to institutional guidelines.
- Antiviral therapy such as acyclovir may be administered if medically appropriate.
- Concomitant treatment with bisphosphonates will be permitted, as appropriate.
- Patients who experience worsening neuropathy from baseline may be observed for recovery, and have dose reductions/delays as indicated in the protocol, and any supportive therapy or intervention may be initiated as appropriate at the discretion of the investigator.
- Supportive measures consistent with optimal patient care may be given throughout the study.

Other medications considered necessary for the patient's safety and well-being may be given at the discretion of the Investigator with the exception of those listed in Section 5.3.2.

CONFIDENTIAL

STUDY DRUG: MLN9708

SCRI INNOVATIONS STUDY NUMBER: MM 42

FINAL PROTOCOL: 11 APRIL 2014

AMENDMENT NUMBER 3: 11 FEBRUARY 2016

VERSION 4

5.3.2 Prohibited Concomitant Medications and Procedures

The following treatments are prohibited while in this study:

- No other investigational therapy should be given to patients.
- Systemic treatment with any of the following metabolizing enzyme inhibitors is not permitted in this study. A DDI with a strong inhibitor would increase MLN2238 exposure:
 - Strong inhibitors of CYP1A2: fluvoxamine, ciprofloxacin, and enoxacin
 - Moderate inhibitors of CYP1A2: mexiletine, propafenone, and zileuton
 - Strong inhibitors of CYP3A: clarithromycin, telithromycin, itraconazole, voriconazole, ketoconazole, posaconazole and nefazodone
 - Moderate inhibitors of CYP3A: amprenavir, aprepitant, diltiazem, erythromycin, fosamprenavir, grapefruit-containing products (including grapefruit juice), and verapamil
- Systemic treatment with any of the following metabolizing enzyme inducers is not permitted in this study:
 - Clinically significant CYP3A inducers: rifampin, rifapentine, rifabutin, carbamazepine, oxcarbazepine, primidone, phenytoin, and phenobarbital

For the most updated information, visit the following website:

<http://medicine.iupui.edu/clinpharm/ddis/>.

- Herbal preparations/medications are not allowed throughout the study. These herbal medications include, but are not limited to: St. John's wort, kava, ephedra (ma huang), ginkgo biloba, dehydroepiandrosterone (DHEA), yohimbe, saw palmetto, and ginseng. Patients should stop using these herbal medications 7 days prior to first dose of study drug.

The following procedures are prohibited during the study:

- No anticancer agents should be given to patients. If such agents are required for a patient, then the patient must first be withdrawn from the study. Adjuvant hormone therapy for breast or prostate cancer
- Radiation therapy (the requirement for local radiation therapy generally indicates disease progression).
- Platelet transfusions to help patients meet eligibility criteria or pre-dose for dosing decisions on treatment are not allowed within 3 days before study drug dosing.

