6.1 Dose Modifications Due to Hematologic Toxicity

Dose reductions or holds and initiation of supportive care are allowed as clinically indicated by the treating physician. Patients whose treatment is delayed due to toxicity will discontinue study drug or will proceed with the next cycle of treatment when toxicity has improved (as long as the toxicity resolves within 3 weeks) according to the dose modifications below. Treatment with MLN9708 will be held in any patient experiencing a DLT as described in Section 5.1.2 at any time during the study. Patients who experience a DLT in the first cycle of therapy will be discontinued from treatment with MLN9708. Dose modifications following treatment-related toxicity in subsequent cycles will be according to the dose modifications below.

Dose reductions for toxicity will be allowed. For patients in the first cohort, MLN9708 may be delayed, but not reduced. For patients in Cohorts 2 and 3, doses will first be delayed and then

CONFIDENTIAL

STUDY DRUG: MLN9708

SCRI INNOVATIONS STUDY NUMBER: MM 42

FINAL PROTOCOL: 11 APRIL 2014

AMENDMENT NUMBER 3: 11 FEBRUARY 2016

VERSION 4

reductions will be allowed based on clinical judgment of the treatment physician (see Figure 1). If persistent toxicity occurs despite dose delays and/or reductions, the patient will be removed from the study.

Any patients who require a treatment delay of more than 3 weeks due to treatment-related toxicity will be discontinued from study treatment, unless the treating physician and the Study Chair agree that continued treatment at lower doses is in the best interest of the patient.

6.1.1 Recommended MLN9708 Criteria for Beginning or Delaying a Subsequent Treatment Cycle & Dose Modifications for Treatment Associated Toxicity on Day 1 of a New Cycle

Treatment with MLN9708 will use a cycle length of 28 days. For a new cycle of treatment to begin, the patient must meet the following criteria:

- ANC must be $\geq 1,000/\text{mm}^3$.
- Platelet count must be $\geq 40,000/\text{mm}^3$.
- All other nonhematologic toxicity (except for alopecia) must have resolved to \leq Grade 1 or to the patient's baseline condition

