7.4 Response Assessments

Patients will be re-evaluated for response to treatment after 2 cycles of treatment. Response will be assessed at 8-week intervals (± 1 week) during study treatment. Patients with progressive disease (PD) or unacceptable toxicity should be discontinued from the study; patients with stable disease (SD) or response to therapy will continue treatment through 6 cycles.

The following assessments will be performed as clinically indicated:

- Bone marrow aspirate and biopsy (to confirm CR only) including:
 - Quantify percent myeloma cell involvement
 - Obtain bone marrow aspirate for cytogenetics [i.e., diploidy, del 13] and include number of metaphases analyzed

CONFIDENTIAL

STUDY DRUG: MLN9708
 FINAL PROTOCOL: 11 APRIL 2014
 AMENDMENT NUMBER 3: 11 FEBRUARY 2016

SCRI INNOVATIONS STUDY NUMBER: MM 42

VERSION 4

- Mutations detected in FISH studies [i.e., t(4:14); t(11:14); del 17p]
- If available, provide MRD by flow cytometry
- SFLC
- SPEP and serum protein immunofixation to determine M-protein
- UPEP, urine protein immunofixation (requires a 24-hour urine collection), and total protein in urine
- Serum quantitative immunoglobulins
- Known plasmacytomas, utilize same modality used to assess original disease (i.e., PET, MRI, CT, etc)

Above response assessment will be performed every 3 months for 2 years after completion of maintenance therapy until disease progression.

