- ^m Bone marrow aspirate and biopsy – quantify percent myeloma cell involvement, and obtain bone marrow aspirate for cytogenetics [i.e., diploidy, del(13)] and FISH studies [i.e., t(4:14); t(11:14);del(17p)], and at the response assessments to confirm CR only. If available, provide MRD by flow cytometry at baseline.
- ⁿ Skeletal survey (lateral radiograph of the skull, anteroposterior and lateral views of the spine, and anteroposterior views of the pelvis, ribs, femora, and humeri) ≤ 28 days of first study drug treatment. Only repeat if clinically indicated (i.e., bone pain).
- ^o UPEP requires the collection of a 24-hour urine sample.
- ^p Repeat if abnormal at baseline.
- ^q All patients will undergo the end of treatment visit assessments listed within 30 days after treatment ends due to completion of the planned study treatment period, or once a patient is discontinued due to unacceptable toxicity or decision to discontinue treatment by the patient or the study physician. If treatment is discontinued because of toxicity or any other reason(s) at a treatment visit and no study treatment is administered, that visit may fulfill the End of Treatment Visit. After withdrawal from or completion of protocol treatment, patients must be followed for AEs for 30 calendar days after the last dose of study drug.
- ^r Patients who discontinue study treatment prior to the occurrence of disease progression will be followed every 3 months during years 1 and 2.
- ^s After disease progression is documented, patients will be followed every 3 months during years 1 and 2 for survival assessment.
- ^t For known plasmacytomas, utilize the same modality used to assess original disease (i.e., PET, MRI, CT, etc).
-

CONFIDENTIAL

STUDY DRUG: MLN9708

SCRI INNOVATIONS STUDY NUMBER: MM 42

FINAL PROTOCOL: 11 APRIL 2014

AMENDMENT NUMBER 3: 11 FEBRUARY 2016

VERSION 4

Page 79 of 86

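### Five places take patients out of the study where section 3.3 only stops study treatment; read literally with an on-study definition of death, this would censor OS informatively

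*Protocol*

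**What the plan says.** **Wording that takes patients out of the study**

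- Protocol 5.3.2, when another anticancer agent is needed: "If such agents are required for a patient, then the patient must first be withdrawn from the study".
- Protocol 6.1, when toxicity persists despite delays or reductions: "the patient will be removed from the study".
- Protocol 7.4: "Patients with progressive disease (PD) or unacceptable toxicity should be discontinued from the study". Appendix D note f and the efficacy assessment timepoints box of the SAP (section 5/6) repeat this.

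**Wording that stops only study treatment, or provides for follow-up**

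- Protocol 3.3: "Patients will be discontinued from study treatment for any of the following reasons". The list includes progression, intolerable toxicity and "Conditions requiring therapeutic intervention not permitted by the protocol". Withdrawal of consent from the study is a separate item.
- Appendix D, before progression: "Patients who discontinue study treatment prior to the occurrence of disease progression will be followed every 3 months during years 1 and 2". After progression: "After disease progression is documented, patients will be followed every 3 months during years 1 and 2 for survival assessment".
- Protocol 11.3.4 refers to survival follow-up after the study and names an eCRF screen for it.

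**The OS event**

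Protocol 10.4.2 and SAP 1.2 define the OS event as a death on study. The OS table in SAP section 5/6 counts a death on study or in follow-up, and censors everyone else at the date last known alive.

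**The concern.** The same clinical situation has two different consequences for follow-up, depending on which section a site opens. A patient who needs salvage therapy is withdrawn from the study under 5.3.2 but only stops study treatment under 3.3. No sentence says that a patient withdrawn under 5.3.2 or removed under 6.1 stays in survival follow-up. The pre-progression follow-up note in Appendix D is written for patients who stop study treatment, not for patients withdrawn from the study.

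A site that reads 5.3.2 or 6.1 literally could stop contacting the patient. An analyst who reads protocol 10.4.2 or SAP 1.2 literally could leave out a death that was recorded in follow-up. Either way the patient is censored when new therapy starts or toxicity forces a stop, which is when the outlook is likely to differ from that of patients who remain. Kaplan-Meier assumes that censoring carries no information about prognosis, and this censoring would. Two-year OS is a secondary objective, and with at most 38 patients a few losses can move it visibly.

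**Working it through.** **1. The plan's own figure.** Three cohorts of at most 6 give 3 × 6 = 18, and 18 + 20 in expansion = 38, as the synopsis states. The plan gives no power, alpha or effect size for OS, so there is no OS design figure to reproduce.

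**2. The passages side by side.**

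| Situation | Out of the study | Off study treatment only | Follow-up afterwards |
|---|---|---|---|
| Other anticancer agent needed | 5.3.2 | 3.3 (therapy not permitted by the protocol) | Appendix D follow-up notes |
| Persistent or unacceptable toxicity | 6.1, 7.4, note f, SAP box | 3.3 | Appendix D, pre-progression note |
| Progression | 7.4, note f, SAP box | 3.3 | Appendix D, post-progression note; 11.3.4 |

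The terms are mixed inside single sections. Section 3.3 is about stopping treatment but goes on to ask for the reason for withdrawal from the study. Appendix D schedules visits for patients it calls off study, yet its note f discontinues patients from the study. The survival status row in Appendix D appears to be marked only in the post-progression column. If so, survival for a patient who starts another agent before progression rests on the general 3-monthly visits. Check this against the original table layout.

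**3. Timing.** Enrolment is at Days 45 to 120 after transplant. Taking Day 1 as the enrolment day, two years after transplant falls 730 − 120 = 610 to 730 − 45 = 685 days after Day 1. Treatment lasts 6 × 28 = 168 days. A patient lost during treatment is therefore lost well before the landmark.

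**4. Size if a share of patients is lost.** Assumptions, not from the documents: a share w leaves alive early and is censored; 2-year OS is 70% in those who stay and s in those who leave. Kaplan-Meier then tends to 70%, while full follow-up gives (1 − w) × 70% + w × s. The overstatement is w × (70% − s).

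| w | s = 70% | s = 50% | s = 30% |
|---|---|---|---|
| 10% | 0 | 2 | 4 |
| 20% | 0 | 4 | 8 |
| 30% | 0 | 6 | 12 |
| 40% | 0 | 8 | 16 |

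(Percentage points.) With equal survival in both groups there is no bias, only lost precision. The 95% half-width is 1.96 × √(0.7 × 0.3 / n). At n = 38 it is 14.6 points. With 10% to 40% lost, n becomes 38 × (1 − w) and the half-width 15.4 to 18.8 points. For the 20 expansion patients alone it rises from 20.1 to 21.2-25.9 points.

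**5. Extreme case: every patient lost at new therapy.** Assume constant monthly hazards: a for progression or new therapy, b for death before it, c for death after it. True survival at t = 24 months is

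exp(−(a+b)t) + [a / (a+b−c)] × [exp(−ct) − exp(−(a+b)t)].

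- a = 0.02, b = 0.008, c = 0.035: 0.511 + (−2.857)(0.432 − 0.511) = 0.736.
- a = 0.03, b = 0.008, c = 0.05: 0.402 + (−2.5)(0.301 − 0.402) = 0.653.

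The final values come from unrounded terms. Censoring everyone at new therapy gives exp(−0.008 × 24) = 0.825 in both cases. The overstatement is 0.825 − 0.736 = 9 points and 0.825 − 0.653 = 17 points.

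**The case against.** The strongest reply is that the documents plainly intend follow-up to continue. Appendix D has a follow-up column for patients who are off study and have not progressed, so in this protocol off study does not mean out of contact. Its notes schedule 3-monthly follow-up in years 1 and 2 both before and after progression. Section 7.4 itself goes on to schedule response assessments every 3 months for 2 years after maintenance until progression. Section 11.3.4 provides for survival follow-up after the study. The SAP's OS table counts deaths in follow-up, and its PFS table has rows for patients who received subsequent therapy and then died on study, so the analysts expected data after new therapy. Section 12.3.1.1 asks sites to seek vital status even from patients who revoke authorization. This stands. A reader might infer from 5.3.2 that the protocol cuts off survival follow-up, and the documents do not support that.

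A reader might also infer that progressions after stopping for toxicity drop out of PFS because of this wording. They do not. Appendix D schedules response assessment for patients off study before progression. What censors those patients is the SAP's own PFS row for treatment discontinuation for an adverse event or other non-event reason, and rewording the five places would leave that row as it is.

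Appendix D is also not cleanly the opposing text, because its note f repeats the from-the-study wording. That is fair, but it shows that the term is unstable rather than that it is clear. Lastly, OS is a descriptive secondary endpoint in a single-arm study, which limits the stakes.

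**Conclusion.** The point holds as an inconsistency to reconcile. Five places take patients out of the study where section 3.3 stops only study treatment, and the OS event is defined in two ways. The plan does provide for follow-up, so bias arises only if a site or an analyst applies the narrower wording literally. Nothing in the text expressly prevents that for patients withdrawn under 5.3.2 or removed under 6.1.

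If it happened, 2-year OS would be overstated whenever the lost patients fare worse than those who remain. The size is about 0 to 16 points with 10-40% lost, and 9 to 17 points if every patient were lost at new therapy. The two ranges come from different models. All survival values, hazards and loss shares are assumed, so neither range is a forecast. The second would require every site to disregard the explicit post-progression survival visits in Appendix D. The correction is worth making because it costs little and protects a stated objective.

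**What to change.** 1. In protocol 5.3.2, 6.1, 7.4, Appendix D note f and the SAP's efficacy assessment timepoints box, say that the patient is discontinued from study treatment and followed per Appendix D.
2. Reserve study withdrawal for withdrawal of consent to follow-up or loss to follow-up, and say so in section 3.3.
3. State in Appendix D that survival status is collected in both follow-up columns, including for patients who start another agent before progression.
4. In protocol 10.4.2 and SAP 1.2, define the OS event as death from any cause, on study or in follow-up, to match the SAP's OS table.

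The sample size stays at 38, and no treatment-stopping or dosing rule changes. The 3-monthly visits are already in Appendix D, so the cost is a wording amendment to the protocol and SAP, plus a survival status entry at pre-progression visits if it is not already collected there. The documents do not say how the visits are funded; section 12.4 leaves finances to a separate agreement.
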